11.1.7 Response Review

Radiological images will be collected for a possible review of response by an expert(s) independent of the study. Measurement of tumor response by a trained radiologist/nuclear medicine physician at each clinical site will be chronicled and reported unless or until a central expert review takes place.

11.2 Other Response Parameters: Immune-Related Response Criteria (irRC)

See [Appendix C](#) for a detailed description of the evaluation criteria.

12. STUDY OVERSIGHT AND DATA REPORTING / REGULATORY REQUIREMENTS

Adverse event lists, guidelines, and instructions for AE reporting can be found in [Section 7.0](#) (Adverse Events: List and Reporting Requirements).

12.1 Study Oversight

This protocol is monitored at several levels, as described elsewhere in this section. The Protocol PI is responsible for monitoring the conduct and progress of the clinical trial, including the ongoing review of accrual, patient-specific clinical and laboratory data, and routine and serious AEs; reporting of expedited AEs; and accumulation of reported AEs from other trials testing the same drug(s). The Protocol PI and statistician have access to the data at all times.

All Study Investigators at participating sites who register/enroll patients on a given protocol are responsible for timely submission of data via the mechanism described elsewhere in this section. All studies are also reviewed in accordance with the enrolling institution's data safety monitoring plan.

12.2 Data Submission/Reporting

Medidata Rave is a clinical data management system being used for data collection for this trial/study. Access to the trial in Rave is controlled through the CTEP-IAM system and role assignments.

Requirements to access Rave via iMedidata:

- A valid CTEP-IAM account; and
- Assigned a Rave role on the LPO or PO roster at the enrolling site of: Rave CRA, Rave Read Only, Rave CRA (LabAdmin), Rave SLA, or Rave Investigator.

Rave role requirements:

- Rave CRA or Rave CRA (Lab Admin) role must have a minimum of an Associate Plus (AP) registration type;
- Rave Investigator role must be registered as an Non-Physician Investigator (NPIVR) or Investigator (IVR); and
- Rave Read Only role must have at a minimum an Associates (A) registration type.

Refer to <https://ctep.cancer.gov/investigatorResources/default.htm> for registration types and documentation required.

This study has a Delegation of Tasks Log (DTL). Therefore, those requiring write access to Rave must also be assigned the appropriate Rave tasks on the DTL.

Upon initial site registration approval for the study in Regulatory Support System (RSS), all persons with Rave roles assigned on the appropriate roster will be sent a study invitation email from iMedidata. To accept the invitation, site users must either click on the link in the email or log in to iMedidata via the CTSU members' website under Data Management > Rave Home and click to accept the invitation in the Tasks pane located in the upper right corner of the iMedidata screen. Site staff will not be able to access the study in Rave until all required Medidata and study specific trainings are completed. Trainings will be in the form of electronic learnings (eLearnings) and can be accessed by clicking on the eLearning link in the *Tasks* pane located in the upper right corner of the iMedidata screen. If an eLearning is required for a study and has not yet been taken, the link to the eLearning will appear under the study name in the *Studies* pane located in the center of the iMedidata screen; once the successful completion of the eLearning has been recorded, access to the study in Rave will be granted, and a *Rave EDC* link will replace the eLearning link under the study name.

Site staff that have not previously activated their iMedidata/Rave account at the time of initial site registration approval for the study in RSS will also receive a separate invitation from iMedidata to activate their account. Account activation instructions are located on the CTSU website, Rave tab under the Rave resource materials (Medidata Account Activation and Study Invitation Acceptance). Additional information on iMedidata/Rave is available on the CTSU members' website under the Rave tab at www.ctsu.org/RAVE/ or by contacting the CTSU Help Desk at [name] or by email at [contact].

12.2.1 Method

This study will be monitored by the CTMS. Data will be submitted to CTMS at least once every 2 weeks via Medidata Rave (or other modality if approved by CTEP).

Information on CTMS reporting is available at:

<http://www.theradex.com/clinicalTechnologies/?National-Cancer-Institute-NCI-11>.

For CTMS monitored studies, after users have activated their accounts, please contact the Theradex Help Desk at [contact] or by email at [contact] for additional support with Rave and completion of CRFs.

12.2.2 Responsibility for Data Submission

For trials monitored by CTMS, a quarterly report of data will be provided by Theradex to the Coordinating Center.

12.3 CTEP Multicenter Guidelines

This protocol will adhere to the policies and requirements of the CTEP Multicenter Guidelines. The specific responsibilities of the PI and the Coordinating Center (Study Coordinator) and the procedures for auditing are presented in [Appendix B](#).

- The Principal Investigator/Coordinating Center is responsible for distributing all IND Action Letters or Safety Reports received from CTEP to all participating institutions for submission to their individual IRBs for action as required.
- Except in very unusual circumstances, each participating institution will order DCTD-supplied agents directly from CTEP. Agents may be ordered by a participating site only after the initial IRB approval for the site has been forwarded by the Coordinating Center to the CTEP PIO ([contact]) except for Group studies.

12.4 Collaborative Agreements Language

The agent(s) supplied by CTEP, DCTD, NCI used in this protocol is/are provided to the NCI under a Collaborative Agreement (CRADA, CTA, CSA) between the Pharmaceutical Company(ies) (hereinafter referred to as “Collaborator(s)”) and the NCI Division of Cancer Treatment and Diagnosis. Therefore, the following obligations/guidelines, in addition to the provisions in the “Intellectual Property Option to Collaborator” (http://ctep.cancer.gov/industryCollaborations2/intellectual_property.htm) contained within the terms of award, apply to the use of the Agent(s) in this study:

1. Agent(s) may not be used for any purpose outside the scope of this protocol, nor can Agent(s) be transferred or licensed to any party not participating in the clinical study. Collaborator(s) data for Agent(s) are confidential and proprietary to Collaborator(s) and shall be maintained as such by the investigators. The protocol documents for studies utilizing Agents contain confidential information and should not be shared or distributed without the permission of the NCI. If a copy of this protocol is requested by a patient or patient’s family member participating on the study, the individual should sign a confidentiality agreement. A suitable model agreement can be downloaded from: <http://ctep.cancer.gov>.
2. For a clinical protocol where there is an investigational Agent used in combination with (an)other Agent(s), each the subject of different Collaborative Agreements, the access to and use of data by each Collaborator shall be as follows (data pertaining to such combination use shall hereinafter be referred to as "Multi-Party Data"):

- a. NCI will provide all Collaborators with prior written notice regarding the existence and nature of any agreements governing their collaboration with NCI, the design of the proposed combination protocol, and the existence of any obligations that would tend to restrict NCI's participation in the proposed combination protocol.
- b. Each Collaborator shall agree to permit use of the Multi-Party Data from the clinical trial by any other Collaborator solely to the extent necessary to allow said other Collaborator to develop, obtain regulatory approval, or commercialize its own Agent.
- c. Any Collaborator having the right to use the Multi-Party Data from these trials must agree in writing before the commencement of the trials that it will use the Multi-Party Data solely for development, regulatory approval, and commercialization of its own Agent.

3. Clinical Trial Data and Results and Raw Data developed under a Collaborative Agreement will be made available to Collaborator(s), the NCI, and the FDA, as appropriate and unless additional disclosure is required by law or court order as described in the IP Option to Collaborator (http://ctep.cancer.gov/industryCollaborations2/intellectual_property.htm). Additionally, all Clinical Data and Results and Raw Data will be collected, used and disclosed consistent with all applicable federal statutes and regulations for the protection of human subjects, including, if applicable, the *Standards for Privacy of Individually Identifiable Health Information* set forth in 45 C.F.R. Part 164.
4. When a Collaborator wishes to initiate a data request, the request should first be sent to the NCI, who will then notify the appropriate investigators (Group Chair for Cooperative Group studies, or PI for other studies) of Collaborator's wish to contact them.
5. Any data provided to Collaborator(s) for Phase 3 studies must be in accordance with the guidelines and policies of the responsible Data Monitoring Committee (DMC), if there is a DMC for this clinical trial.
6. Any manuscripts reporting the results of this clinical trial must be provided to CTEP by the Group office for Cooperative Group studies or by the PI for non-Cooperative Group studies for immediate delivery to Collaborator(s) for advisory review and comment before submission for publication. Collaborator(s) will have 30 days from the date of receipt for review. Collaborator shall have the right to request that publication be delayed for up to an additional 30 days in order to ensure that Collaborator's confidential and proprietary data, in addition to Collaborator(s)'s intellectual property rights, are protected. Copies of abstracts must be provided to CTEP for forwarding to Collaborator(s) for courtesy review as soon as possible and preferably at least three (3) days before submission, but in any case, before presentation at the meeting or publication in the proceedings. Press releases and other media presentations must also be forwarded to CTEP before release. Copies of any manuscript, abstract and/or press release/ media presentation should be sent to:

Email: [contact]

The Regulatory Affairs Branch will then distribute them to Collaborator(s). No publication, manuscript or other form of public disclosure shall contain any of Collaborator's confidential/proprietary information.

12.5 Genomic Data Sharing Plan: N/A

13. STATISTICAL CONSIDERATIONS

This section outlines the statistical analysis strategy and methods for the study. If, after the study has begun, but before the conduct of any analysis, changes are made to primary and/or key secondary hypotheses or the statistical methods related to those hypotheses, then the protocol will be amended (consistent with ICH Guideline E-9). Changes to exploratory or other non- confirmatory analyses made after the protocol has been finalized, along with an explanation as to when and why they occurred, will be listed in the Clinical Study Report (CSR) for the study. Post hoc exploratory analyses will be clearly identified in the CSR. No separate Statistical Analysis Plan (SAP) will be issued for this study.

13.1 Responsibility for Analyses

The statistical analysis of the data obtained from this study will be the responsibility of Fred Hutch as part of the CITN.

13.2 Study Design/Objectives

This is a phase II trial of atezolizumab (MPDL3280A) plus recombinant human IL-7 (CYT107) in patients with locally advanced or metastatic urothelial carcinoma. The trial follows a randomized, controlled trial design, with an initial 'Safety Run-In' phase designed to evaluate the acute safety profile of the investigational treatment combination. The Safety Run-In phase is designed to demonstrate that the incidence of DLTs is 16.7% or less in 6 patients receiving the investigational combination. These patients will not be included as part of the overall analysis since they are not randomized. Due to the non-randomized nature of the enrollment for these six patients, the inclusion of these patients in the overall analysis could confound and bias results of any randomized comparisons. Hence, these 6 patients will be analyzed and reported separately both for safety and for efficacy. However, toxicity data from all patients will be reviewed in the aggregate at the time of the interim and final analysis to evaluate overall patterns.

The randomized trial is designed to evaluate the improvement in the objective response rate (ORR) of CYT107 + atezolizumab compared to atezolizumab alone in patients with advanced/unresectable bladder cancer who have progressive disease after a platinum-based chemotherapy regimen. An interim futility analysis will be conducted when 50% of planned sample size have their first disease assessment and survival information. An exploratory analysis will be conducted to evaluate the ORR after all patients have been followed up for 2 years.

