5. TREATMENT PLAN

This is a phase II trial of atezolizumab (MPDL3280A) plus recombinant human IL-7 (CYT107) in patients with locally advanced or metastatic urothelial carcinoma. The trial follows a randomized, controlled trial design, with an initial 'Safety Run-In' phase designed to evaluate the acute safety profile of the investigational treatment combination.

During the Safety Run-In phase, 6 patients will be assigned to the experimental arm (atezolizumab + CYT107) with staggered enrollment. This will be accomplished with an initial 3 patient enrollment. All adverse events will be assessed by the Toxicity Evaluation Committee. If 0-1 patient experiences a protocol-defined DLT (refer to [Section 5.2](#)) after completion of the 4-week DLT window, an additional 3 patients will be enrolled. Once all 6 patients have completed the 4-week DLT window, the Toxicity Evaluation Committee will again assess all adverse events. If, at any time, 2 or more patients experience a protocol-defined DLT, further enrollment into the trial will be suspended.

If the treatment combination of the experimental arm demonstrates an acceptable safety profile in the Safety Run-In (one or fewer patient experiences a protocol-defined DLT), randomized enrollment into the trial will begin.

Patients will be randomly assigned to either the control arm (atezolizumab monotherapy) or experimental arm (atezolizumab + CYT107) of the trial.

The first 6 subjects enrolled in the run-in phase of the study will have PK sampling done at baseline (prior to CYT107 administration), and at week 4 prior to CYT107 administration and at 2 hours, 4 hours and 6 hours after the fourth CYT107 administration.

Anti-drug antibody testing (ADA testing) will be done on all subjects who receive CYT107. Testing will be done at baseline (prior to CYT107 administration) and at week 8, (1 month after

the last CYT107 administration.) Any subject who develops binding antibodies will be further tested for the presence of anti-CYT107 neutralizing antibodies.

Randomization in the OPEN system may be performed up to 5 business days before initiation of study treatment to allow for clinical site logistics.

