5.2.2 Non-hematologic toxicity

Any Grade ≥ 3 non-hematologic toxicity (CTCAE v5.0), ***except*** for the following, which will not constitute DLTs:

- Grade ≥ 3 nausea or vomiting lasting ≤ 72 hours with the use of adequate/maximal medical intervention and/or prophylaxis

- Grade 3 diarrhea lasting \leq 72 hours with the use of adequate/maximal medical intervention and/or prophylaxis
- Grade 3 fatigue lasting \leq 7 days
- Grade 3 injection site reaction (unless operative intervention is required)
- Grade 3 hyperglycemia lasting \leq 72 hours with standard antidiabetic therapy
- Grade 3 increases in liver transaminases ($>5.0-20.0 \times$ ULN) in patient with liver metastases
- Clinical laboratory abnormalities that are reversible to \leq Grade 1 or baseline status within 72 hours with outpatient care and/or monitoring, or that are considered not clinically significant by the treating physician

Management and dose modifications associated with the above AEs are outlined in [Section 6](#).

The AEs will be assessed by the Toxicity Evaluation Committee, which includes the PI(s), study sponsor(s), CTEP and the CITN Central Operating and Statistical Center (COSC).

The patients must complete the full 4-week DLT window to be considered evaluable for DLTs. Patients who discontinue from the study before completion of the full 4-week DLT window for reasons other than the occurrence of a DLT (e.g., withdrawal of consent, rapid tumor progression, death due to rapid tumor progression, AE that does not meet DLT criteria) will not be considered evaluable for DLTs and will be replaced.

All randomly assigned patients will be monitored for occurrence of DLT. Monitoring of all safety and toxicity data is done by the PI, the study Sponsor(s) and the CITN COSC on a real-time basis as data are entered into Medidata Rave using the Web Reporting Module. All participating sites must notify the PI and CITN COSC when a DLT has occurred.

A delay due to toxicity in receiving the second cycle of therapy of >14 days will be considered a DLT in subjects enrolled in the safety run-in phase of the study. This does not apply to subsequent subjects enrolled in the randomized component of the study.

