13.3 Sample Size/Accrual Rate

During the Safety Run-In phase, 6 patients will be assigned to the experimental arm (atezolizumab + CYT107) with staggered enrollment (refer to [Section 5](#) for details). The AEs will be assessed by the Toxicity Evaluation Committee. If, at any time, 2 or more patients experience a protocol-defined DLT (refer to [Section 5.2](#)), further enrollment into the trial will be suspended.

If the treatment combination of the experimental arm demonstrates an acceptable safety profile in the Safety Run-In (1 or fewer patient experiences a protocol-defined DLT), randomized enrollment into the trial will begin.

A total of 54 patients will be enrolled in this study; 6 patients in the Safety Run-In and 48 patients in the randomized portion of the study. The expected accrual is 4 patients per month total at approximately 8 CITN sites. A study with 48 randomly assigned patients (1:1 randomization) will meet the following statistical parameters: $H_{\text{null}} = 14.8\%$; $H_{\text{alt}} = 45\%$; one-sided alpha of 0.10; power 88%.

The interim futility analysis will be conducted when 24 randomized patients have their first disease assessment and survival information. The futility analysis is based on an O'Brien-Fleming boundary, and the futility boundary will be considered to be crossed when the difference of ORR in the experimental arm – ORR in the control arm is less than -0.0063. Under the null hypothesis, the probability of crossing the futility boundary is 48.2%.

Safety Population: All patients who receive at least 1 dose of the investigational regimen will be considered evaluable for safety and included in the overall safety analysis. For the Safety Run-in phase, in the absence of a DLT, patients must complete the full 28-day DLT window period to be considered evaluable for DLTs. Patients who discontinue from the study before the completion of the full 28-day DLT window for reasons other than the occurrence of a DLT (e.g., withdrawal of consent, rapid tumor progression, death due to rapid tumor progression, AE that does not meet DLT criteria) will not be considered evaluable for DLTs and will be replaced.

Efficacy Population: The efficacy analysis will be conducted on all randomized patients, based upon the intent-to-treat population.

PLANNED ENROLLMENT REPORT

Racial Categories	Ethnic Categories		Totals
	Not Hispanic or Latino	Hispanic or Latino	

	Female	Male	Female	Male	
American Indian/ Alaska Native	1	2			3

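### Section 13.2 says the six-patient run-in demonstrates a DLT incidence of 16.7% or less, but 16.7% is only the observed go cut-off of 1 in 6, and no passing result shows a true rate that low

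*Combined protocol and SAP*

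**What the plan says.** Section 13.2 (Study Design/Objectives) gives the statistical aim of the run-in: it is "designed to demonstrate that the incidence of DLTs is 16.7% or less in 6 patients receiving the investigational combination".

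The operating rule is in Sections 5 and 13.3.

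- Size: "During the Safety Run-In phase, 6 patients will be assigned to the experimental arm (atezolizumab + CYT107) with staggered enrollment".
- Staging (Section 5): "This will be accomplished with an initial 3 patient enrollment". A further 3 are enrolled if 0 or 1 of the first 3 has a DLT.
- Stop (Section 5): "If, at any time, 2 or more patients experience a protocol-defined DLT, further enrollment into the trial will be suspended".
- Go (Section 13.3): the combination "demonstrates an acceptable safety profile in the Safety Run-In (1 or fewer patient experiences a protocol-defined DLT") and randomization then begins.

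Section 5.2.2 requires run-in patients to complete the DLT window to be evaluable. Those who leave early without a DLT are replaced, so the denominator stays at 6.

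After the run-in, Section 5.2.2 states: "All randomly assigned patients will be monitored for occurrence of DLT". It also provides for real-time safety review and requires sites to notify each DLT. Section 13.2 has the six run-in patients analysed and reported separately, and has toxicity from all patients reviewed in aggregate at the interim and final analyses.

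No confidence level, error rate, unacceptable DLT rate or operating characteristics are given for the run-in. Section 13 says that no separate SAP will be issued, so no later analysis document will qualify the sentence.

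**The concern.** A design that demonstrates an incidence at or below a threshold would normally be one in which a passing result excludes higher true rates with stated confidence. Six patients cannot do that at 16.7%. The number matches 1/6 exactly, which suggests that the go cut-off has been restated as a property of the design.

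The sentence matters because a pass is what opens randomization of a new combination to 24 more patients on the experimental arm (48 randomized 1:1). If it is read at face value, the run-in could be described as having shown more about the DLT rate than it can.

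**Working it through.** **Inputs.** From the protocol: n = 6 evaluable patients, pass at 0 or 1 DLT, suspend at 2 or more at any time, enrolled 3 + 3 (Sections 5, 5.2.2, 13.3); 48 patients randomized 1:1 (Section 13.3). Assumed here: the true DLT rates p in step 2 and the confidence levels in steps 3 to 5. The documents give neither.

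**1. The plan's own figure.** 1/6 = 0.1667 = 16.7%. It is the largest observed proportion that passes.

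**2. Chance of passing.** With X ~ Binomial(6, p), P(pass) = P(X ≤ 1) = (1 − p)^6 + 6p(1 − p)^5. At p = 0.30 this is 0.7^6 + 6 × 0.3 × 0.7^5 = 0.1176 + 0.3025 = 0.420.

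| Assumed true DLT rate | P(pass) |
|---|---|
| 10% | 0.886 |
| 16.7% | 0.737 |
| 20% | 0.655 |
| 30% | 0.420 |
| 40% | 0.233 |
| 50% | 0.109 |

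Enumerating the 3 + 3 staging with a stop at 2 DLTs gives the same values, because the path passes exactly when the total is 0 or 1. At a true rate of exactly 16.7%, the rule fails 1 − 0.737 = 26% of the time.

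**3. What a pass excludes.** The exact (Clopper-Pearson) one-sided upper limit is the p at which a result this low or lower has probability 5% (or 10%).

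- 0 of 6: (1 − p)^6 = 0.05 gives p = 1 − 0.05^(1/6) = 39.3%. At one-sided 90% it is 31.9%.
- 1 of 6: (1 − p)^6 + 6p(1 − p)^5 = 0.05 gives p = 58.2%. At one-sided 90% it is 51.0%. The two-sided 95% interval is 0.4% to 64.1%.

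All four upper limits are well above 16.7%.

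**4. What excluding 16.7% would take.** With zero DLTs in n patients, (5/6)^n must be at most 0.05, so n ≥ ln 0.05 / ln(5/6) = 16.4, that is 17 patients. At one-sided 90%, n ≥ 12.6, that is 13. This shows the scale of the gap; it is not a proposal to enlarge the run-in.

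**5. What later data would add.** Combination patients number up to 6 + 24 = 30. The same observed proportion, 5/30 = 16.7%, has an exact one-sided 95% upper limit of 32%, against 58% for 1/6.

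**The case against.** The strongest reply is that the sentence claims nothing about a population rate. It says 16.7% or less *in 6 patients*. Read literally, that is an observed proportion of at most 1/6, which restates the go rule. The sentence before it gives the purpose as evaluating acute safety, and no alpha or confidence level is attached. This reading is available. On it the fault is one of wording, and a wording change is what is asked for. It does not remove the point, because incidence together with *demonstrate* invites the inferential reading in the protocol's only statistical section.

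Four stronger inferences are tempting, and the documents do not support them.

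- *That the rule is inconsistent or wrong.* Sections 5, 13.2 and 13.3 agree on at most 1 of 6, and the Toxicity Evaluation Committee assesses all adverse events after 3 patients and again after 6, not only a DLT count.
- *That DLTs after the run-in go unused.* No DLT summary or numerical boundary is specified, but Section 5.2.2 provides real-time monitoring and Section 13.2 an aggregate toxicity review at the interim and final analyses.
- *That a 30% DLT rate is likely.* It is an illustrative value. Section 2.2 reports no DLTs determined for single-agent atezolizumab and none observed in the ongoing CYT107 trial. That does not settle the rate for the combination, but it gives no ground for assuming 30%.
- *That the efficacy result is at risk.* Run-in patients are excluded from the randomized comparison, so the primary ORR test is untouched.

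An objection to simple pooling also stands. Section 5.2.2 counts a toxicity delay of more than 14 days to cycle 2 as a DLT only in the run-in. The evaluability and replacement rule is stated only for the run-in. Section 13.2 requires the six patients to be reported separately. A pooled rate has to respect all three.

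**Conclusion.** The point holds as a misstatement of what the run-in can show. 16.7% is the observed go cut-off, and neither passing result demonstrates a true DLT rate that low: the exact one-sided 95% upper limits are 39% after 0/6 and 58% after 1/6. The limits assume independent patients with a common DLT rate and a confidence level chosen here; at one-sided 90% they are 32% and 51%, and the conclusion is the same. The pass probabilities also depend on assumed true rates.

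The correction is worth making because the sentence describes the gate to randomization and nothing else in the plan qualifies it. It changes no decision rule and no efficacy analysis.

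**What to change.** 1. In Section 13.2, replace the sentence with a statement of the existing rule: randomization opens if at most 1 of 6 evaluable patients has a DLT. Drop *demonstrate*.
2. Add the pass probabilities, labelled illustrative: 89%, 74%, 66%, 42% and 23% at assumed true rates of 10%, 16.7%, 20%, 30% and 40%. Say that no unacceptable rate has been specified.
3. Report the run-in DLT rate with its exact confidence limit.
4. Within the aggregate toxicity review already planned at the interim and final analyses, add a supplementary descriptive DLT rate with exact limit over all combination patients (up to 30). Use only the DLT criteria that apply in both parts, with one evaluability rule applied to both. Show the run-in-only delay item separately, and keep the separate run-in report that Section 13.2 requires.

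The cost is one sentence, one small table and one descriptive summary, with no added patients or visits. DLT occurrence is already monitored in randomized patients, but the common evaluability rule has to be written down. The downside is that the stated claim becomes less favourable.
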